8.4 As Exposed Biochemically and Exercise Compliant Set

A subset of the AEECS based on biochemical verification of smoking status (AEBECS) will be analysed based on actual arm as determined with these additional criteria.

For a subject to be classified as smoking abstinent, in addition to the product use diary with an average cigarette use at max 5 Cigarettes/month the following will be used,

- No CO breath test > 6 ppm at three consecutive visits from V3 onwards.
- Total NNAL concentration < 75.9 pg/mL in spot urine (Berg, et al. 2012) at two or more visits collected from V3 onwards.
- CEMA concentration adjusted for creatinine < 40 ng/mg creat (Claussen, et al. 2019) in spot urine at two or more visits collected from V3 onwards.

The following biochemical verification will be used in addition to the product use diary to further fine tune subjects in the IQOS user group.

- No CO breath test > 6 ppm at three consecutive visits from V3 onwards.
- Total NNAL concentration < 75.9 pg/mL in spot urine at two or more visits collected from V3 onwards.
- CEMA concentration adjust for creatinine < 40 ng/mg creat in spot urine at two or more visits collected from V3 onwards.

8.5 **Protocol Deviations**

All protocol deviations will be listed and also summarized based on the classification of deviation type for subjects in the Safety Set.

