# 9.3 Baseline and Randomization

Table 7 shows the procedures that will be performed at V3. All baseline assessments should be performed before randomization.

Time	Blood Sample	Procedures	Additional Information
Start of Procedure		V3	
		Urine pregnancy test	
Before breakfast/ snack	$\checkmark$	Clinical laboratory parameters (hematology, clinical chemistry and urinalysis)	At least 8 hours of fasting Hematocrit and Hemoglobin results will also be used to calculate blood volume
	$\checkmark$	Biological health markers	At least 8 hours of fasting
	$\checkmark$	Biobank blood collection	Only if optional ICF signed At least 8 hours of fasting
		Breakfast/Snack	
		Biobank saliva and sweat collection	Only if optional ICF signed
		FTND questionnaire	
		Lifestyle questionnaire	
		RPC scale	
		Vital signs (blood pressure, pulse rate, respiratory rate)	After resting for at least 5 minutes in supine position
		ECG	After resting for at least 10 minutes in supine position prior to recording.
		Physical examination	
		Weight, body fat percentage and waist circumference	
		Cough assessment questionnaire (VAS scale, and 3 Likert scales)	
		CO breath test	

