A demonstration of *IQOS* and the mHealth wearable will be done by the site staff during the screening visit. All inclusion and exclusion criteria will be assessed. A VO₂max test will be performed as part of eligibility assessments. All eligible subjects will be invited to come to V2.

Enrollment and Familiarization, V2 (7 ± 1 days prior to V3): Enrollment will take place after confirmation of smoking status (urine cotinine and exhaled CO) and negative urine pregnancy test, alcohol breath test and urine drug screen. After enrollment, vital signs will be assessed and subjects will perform an exercise capacity test for the purpose of familiarization. The exercise test consists of completing a pre-defined work (calories) on a bike ergometer (1). Before leaving the investigational site the subject will receive a mHealth wearable kit and will be trained on how to handle the device. Subjects will be instructed to wear the device all the time. Subjects will also receive a diary to record the daily use of tobacco and nicotine containing products.

Between V2 and V3, subjects having signed the optional section of the ICF will have an interview (by phone or computer) on the topic of health and functioning lasting around 60 minutes.

Baseline and Randomization, V3: Baseline assessments will be performed as listed in Appendix 1. Then, 30-60 min before start of the VO2max test all subjects will smoke a cigarette (only if they are willing to). During the VO2max test at rest and at each 25 W increase, the subject's lactate levels will be determined by capillary blood sampling and the rate of perceived exertion (RPE) will be assessed using the Borg RPE scale. After completing the VO2max test, the subject will rest for 60±5min, after which the exercise capacity test will be performed. After completing exercise tests, total blood volume will be determined.

Subjects will thereafter be randomized into one of the 4 arms. Subjects randomized into *IQOS* arms will receive their *IQOS* starter kit and be trained on how to use the device. Subjects randomized into the SA arm will receive smoking abstinence support and will be allowed to use NRT upon request.

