Acute effect, V4 (7±2 days after V3): Before the VO₂ max test, vital signs, exhaled CO, weight, body-fat and waist circumference measurements will be performed. 30-60 min before start of the VO₂max test subjects in cigarette and *IQOS* arms will smoke a cigarette or use a HeatStick, respectively (only if they are willing to). Subjects' VO₂max, maximal heart rate and maximal work rate will be determined. After completing the VO₂max test, subjects will rest for 60 ± 5 min after which the exercise capacity test will be performed.

Confidentiality Statement

Philip Morris Products SA.	Statistical Analysis Plan	Confidential
P1-EXC-01-EU	Final 2.0	Page 15 of 71
Related to PMI-RRP-WKI-112487		SAP P1-EXC-01-EU

Training program, from V5 (15 \pm 2 days after V3) until V42 (99 \pm 2 days after V3): Subjects randomized into *IQOS*-1, cigarette and SA arms will participate in 38 supervised training sessions during a 12-week period using three different training protocols (Appendix 2).

Subjects randomized to the *IQOS*-2 arm will come for visits once a week for all assessments except the training. Subjects in the *IQOS*-2 arm will consequently only attend the following visits: V5, V7, V9, V14, V16, V19, V23, V28, V30, V33, V35 and V39.

At V14 and V28 (medical visits), safety, biological health marker and exposure marker assessments will be performed for all subjects.

Before each training, the following assessments will be conducted;

- Weight
- Exhaled CO
- 30-60 min before start of the training subjects in cigarette and IQOS arms will smoke a cigarette or use a HeatStick, respectively (only if they are willing to).

All trainings will be performed on a bike ergometer. The training intensity will be adjusted according to the subject's resting heart rate as determined by ECG at V3, and maximal heart rate as determined at the VO2max test at V4 (acute test). The work produced, the work rate and heart rate will be recorded for each training (as described in Objective 3).

Between V42 and V43, subjects having signed the optional section of the ICF will have an interview (by phone or computer) on the topic of health and functioning lasting around 60 minutes.

Training effect, V43 (106±2 days after V3):

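### The biochemically verified set (AEBECS) requires no marker to be below cut-off at the visit analysed, and its CO run rule is ambiguous and covers different time spans in IQOS-1 and IQOS-2

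*SAP*

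**What the plan says.** AEBECS is a subset of the main set, AEECS. To be classed as smoking abstinent (SA), a subject needs a diary with "average cigarette use at max 5 Cigarettes/month" and must meet three marker conditions. The same three conditions are added to the diary for the IQOS group:

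- CO: "No CO breath test > 6 ppm at three consecutive visits from V3 onwards".
- NNAL: "Total NNAL concentration < 75.9 pg/mL in spot urine at two or more visits collected from V3 onwards".
- CEMA: "CEMA concentration adjust for creatinine < 40 ng/mg creat in spot urine at two or more visits collected from V3 onwards".

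Exhaled CO is measured at all visits; the schedule in SAP 13.1 marks V1 to V43 and not V44. The urine markers are measured at V3, V4, V14, V28 and V43 (SAP 3.1, objective 9). V3 is the baseline visit, and protocol 9.3 states: "All baseline assessments should be performed before randomization". The training arms have 38 sessions, V5 to V42. In that period IQOS-2 subjects "only attend the following visits: V5, V7, V9, V14, V16, V19, V23, V28, V30, V33, V35 and V39" (SAP 4.1).

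SAP 9.6.2.2 and 9.6.2.3 rerun on AEBECS the VO2max and exercise capacity models, which estimate effects at V4 and V43. SAP 9.6.2.4 and 9.6.2.5 use the set for health markers and exposure tables. SAP 7 calls the VO2max and exercise capacity analysis exploratory, and AEECS remains the main set (SAP 8).

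**The concern.** The set exists to check self-reported product use against markers. The models it feeds are visit-specific, but none of the three marker conditions names a visit. The two low urine results can come from any of the five collections, and the CO rule looks only at runs.

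The visit matters in this trial. Protocol 4.2 rests the expected benefit on normalised COHb and cites an effect on VO2max after 8 hours of abstinence. The protocol's summary of changes gives CO a half-life of 2 to 8 hours. Exposure at the time of the exercise test is therefore part of what needs verifying, alongside exposure over the period.

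Three things are at stake. AEBECS tables could carry a verified label that the rules do not support at V43. Two programmers could build different sets from the CO sentence. And a rule counted in visits covers different spans of time in IQOS-1 and IQOS-2, which SAP Table 5 compares at V43.

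**Working it through.** **Visit counts.** V5 to V42 is 42 − 5 + 1 = 38 sessions, which reproduces the stated number. Adding V3, V4 and V43 gives 41 CO tests in the training arms. IQOS-2 has 12 + 3 = 15.

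**CO rule.** Let n be the number of tests.
- Reading A: a subject fails only on three successive results above 6 ppm. Each block of three then needs one result at or below 6, so at most n − floor(n/3) can be above.
- Reading B: three successive results at or below 6 ppm are enough. At most n − 3 can be above.

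| Window | n | Reading A | Reading B |
|---|---|---|---|
| Training arms, V3–V43 | 41 | 41 − 13 = 28 (68%) | 38 (93%) |
| Training arms, 4 sessions missed | 37 | 37 − 12 = 25 (68%) | 34 (92%) |
| IQOS-2, V3–V43 | 15 | 15 − 5 = 10 (67%) | 12 (80%) |
| Training arms, V4–V43 | 40 | 40 − 13 = 27 (68%) | 37 (93%) |
| IQOS-2, V4–V43 | 14 | 14 − 4 = 10 (71%) | 11 (79%) |

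The row with missed sessions uses the AEECS minimum of 34 of 38 and treats the remaining tests as consecutive. In every row V43 can be one of the high results.

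**Urine rule.** With five collections, 10 + 10 + 5 + 1 = 26 patterns have at least two low results. Of these, 6 + 4 + 1 = 11 do not include V43. Up to three of the five samples can be above cut-off.

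**A subject who passes.** Take an SA subject with NNAL and CEMA low at V14 and V28, and CO at or below 6 ppm from V4 until a relapse just before V42. CO is above 6 at V42 and V43, a run of two. NNAL and CEMA are above cut-off at V43. SAP 5.5.1 averages the diary over the period and multiplies by 30. Over 106 days, 17 cigarettes give 17 × 30 / 106 = 4.8 per month, within the limit of 5 even if all were smoked in the last week and reported honestly. Every condition is met, although all three markers are above cut-off at the analysed visit. The same gap exists at V4: low urine at V14 and V28 satisfies the urine rule whatever V4 showed.

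**Span by arm.** The training-arm visits covered by each pair of successive IQOS-2 visits from V5, both ends included, are: V5–V7 3, V7–V9 3, V9–V14 6, V14–V16 3, V16–V19 4, V19–V23 5, V23–V28 6, V28–V30 3, V30–V33 4, V33–V35 3, V35–V39 5, V39–V43 5. The minimum is 3. Under reading A, with full attendance, a relapse with high CO throughout that covers two successive IQOS-2 visits and no third gives at least three successive high tests in IQOS-1 (fail) and two in IQOS-2 (pass).

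**Illustration, not an estimate.** Suppose each test is independently high with probability p (an assumption; real results would cluster). The probability of passing reading A is then:

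| p | 41 tests | 15 tests |
|---|---|---|
| 0.1 | 97% | 99% |
| 0.2 | 77% | 92% |
| 0.3 | 45% | 76% |
| 0.5 | 4% | 32% |

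**V3.** Under reading A a high V3 result can only lengthen a run, so including it makes the CO rule slightly stricter. For urine it helps only someone already below cut-off while smoking at least 10 cigarettes a day, which is unlikely.

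**The case against.** The strongest reply is that 28 of 41 is a bound on one criterion taken alone. It needs full attendance and a strict high-high-low pattern, while the subject also has two low NNAL results, two low CEMA results and a low diary count. This stands: the bound shows what the wording permits, not what is likely. The illustration agrees, since a subject high at a random half of 41 tests would rarely pass. For the IQOS group the diary threshold is in SAP Figure 2, which I could not see, so how strict that group's rule is overall cannot be judged here.

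Second, the model already offers COHb at each visit and daily cigarette use as covariates, and CO and exposure markers are tabulated for AEBECS. This is partial cover only. Backward selection can drop those covariates, and a table shows contamination of a group without removing it.

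Third, SAP 5.5 speaks of using the markers to refine product-use allocation in an exploratory analysis and does not claim proof of exposure. That is fair and limits the weight of the point.

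Fourth, with a half-life of hours, CO at V43 says little about 12 weeks of training. This also stands, so a condition at V43 should supplement the period-wide rules and not replace them.

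**Conclusion.** As written, SAP 8.4 does not verify status at the visit analysed. A subject above all three cut-offs at V43 can be in the AEBECS analysis of V43. This follows from the wording under either reading of the CO rule. The worst-case CO counts (28 of 41 and 10 of 15 under reading A; 38 of 41 and 12 of 15 under reading B) assume full attendance and take the CO rule alone.

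The CO rule can also act differently in IQOS-1 and IQOS-2, because three visits cover different lengths of time.

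Four stronger conclusions might be inferred and are not supported:

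- That AEBECS will in fact contain many current smokers. The documents give no basis for a number.
- That the IQOS-1 versus IQOS-2 comparison is biased. The worst-case shares are nearly equal (68% and 67%), and neither the direction nor the size of any effect on VO2max has been shown.
- That counting from V3 is a main weakness. It is a minor flaw of logic, and starting at V4 barely moves the bounds.
- That the main results are in doubt. AEECS does not use these rules.

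The point should be addressed, at the level of an exploratory analysis.

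**What to change.** Keep the cut-offs and the period-wide rules, and amend SAP 8.4 as follows:

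- (a) State which reading of the CO sentence applies, and how a missed visit affects a run.
- (b) For V43 results, also require CO not above 6 ppm and NNAL and CEMA below their stated cut-offs at V43, and say how a missing V43 marker is handled. For V4 results, require the V4 CO, and CEMA if the sponsor can justify it. Do not require NNAL at V4 unless its clearance within one week of switching is justified; the documents give no clearance time.
- (c) Apply the CO run rule only to the visits common to all arms.
- (d) Count from V4, after randomisation.

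No new data are needed, because all three markers are already scheduled at V4 and V43. The cost is SAP wording, programming and a smaller exploratory set, by an amount that cannot be computed from the documents. Step (c) leaves 41 − 15 = 26 training-arm CO tests out of the run rule and could by itself admit or remove some training-arm subjects. With (c) and (d) the bound under reading A is 10 of 14 in every arm. They make the rule equal across arms but not tighter; the tightening comes from (b).

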8.5.1 Major Protocol Deviations

Major protocol deviations are protocol deviations that may significantly impact the completeness, accuracy, and/or reliability of the study data or that may significantly affect a subject's rights, safety, or well-being.

Subjects with major PDs below will be identified to determine whether they will be excluded from any of the analysis sets.

The following general rules will be applied to determine if a deviation was major:

Confidentiality Statement

Philip Morris Products SA.	Statistical Analysis Plan	Confidential
P1-EXC-01-EU	Final 2.0	Page 33 of 71
Related to PMI-RRP-WKI-112487		

- 1. Protocol violations pertaining to inclusion/exclusion criteria will considered major deviations, evaluable if no results or safety is impacted.
- 2. Protocol violations pertaining to ICF will be considered major deviations, evaluable if no results or safety is impacted. If the ICF was not signed then the subject will be major, non-evaluable.
- 3. If a subject was mis-randomized, defined as being administered to the wrong product according to the randomization schedule during the exposure period.
- 4. The subject did not attend a scheduled visit.
- 5. The subject did not record more than 50% of product use questionnaires for an analysis period.

8.5.2 Minor Protocol Deviations

Minor protocol deviations are defined as deviation that does not impact any of the following: (1) the safety of a subject participating the study; (2) the integrity of the data collected for the evaluation of the study; or (3) the overall evaluation and/or interpretation of the outcome of the study, specifically with respect to the primary objective(s).

9 PLANNED STATISTICAL METHODS

9.1 General Considerations

The statistical evaluation will be performed using SAS[®], version 9.3 or later.

Data presentation formats, precision and rounding will consider Section 2.5 of Record ID PMI-RRP-FOR-112420. Continuous variables will be presented with 3 significant digits, however, values above 999 given as integers and will not be rounded to have zeroes at the rightmost digit(s). For example 12345.67 will be presented as 12346 and not as 12300.

9.1.1 Stratified Presentation

Stratification criteria for the evaluation are:

- Randomized study arm Cigarette, IQOS-1, smoking abstinence (SA), IQOS-2) randomized arm.
- Product use (actual arm) i.e. actual product use exposure categorized based on self-reporting and biochemical verification according to Section 5.5.1 "Product Use Pattern":

Confidentiality Statement

Data and information contained in this document are considered to constitute trade secrets and confidential commercial information, and the legal protections provided to such trade secrets and confidential information are hereby claimed under the provisions of applicable law. No part of this document may be publicly disclosed without the written consent of Philip Morris Products S.A

Philip Morris Products SA.	Statistical Analysis Plan	Confidential
P1-EXC-01-EU	Final 2.0	Page 34 of 71
Related to PMI-RRP-WKI-112487		SAP_P1-EXC-01-EU

- o Cigarette,
- o IQOS-1,
- Smoking Abstinence (SA),
- IQOS-2,
- Dual users considered for IQOS-1 (Dual-1),
- Dual users considered for IQOS-2 (Dual-2),
- Cigarette consumption at V1 (10 to 19 cigarettes, more than 19 cigarettes per day)
- Sex (male, female)
- Age (<50, ≥ 50 years i.e. $21 \le Age < 50$ and $50 \le Age \le 65$])

The main stratification criterion for the evaluation is the actual product exposure, whereas data will be listed by randomization arm.

Further stratification by cigarette consumption and sex will be done for the analysis of VO_2max and exercise capacity and where explicitly defined. Further stratification by age and BMI will be done only where explicitly defined (e.g. for demographic data).

The AEECS, AEBECS and the Safety Set will be analyzed by actual study arm (product use exposure). The FAS will be analyzed by randomized study arm.

9.1.2 Descriptive Statistics

Descriptive statistics for continuous variables will include the number of subjects, number and percent of subjects with missing data, the mean and standard deviation, geometric means and coefficient of variation (CV), median, first and third quartiles (Q1 and Q3), minimum and maximum, and 95% confidence interval (CI; based on a t-distribution if not otherwise stated) on the mean for each study arm, and summary across all subjects if appropriate. For categorical variables descriptive statistics will provide the number of observations, absolute frequencies, and relative frequencies (percentages) of the observed values. In addition, the results may be presented as a stratified summary.

9.1.3 Definitions for Statistical Data Analysis

The baseline value for any given parameter will be the last assessment prior to randomization for the subjects randomized to either IQOS, cigarette or SA arms.

Change from baseline (i.e. difference of post baseline value compared to baseline value) will be calculated as: Change from baseline = post baseline value – baseline value.

Confidentiality Statement

Philip Morris Products SA.	Statistical Analysis Plan	Confidential
P1-EXC-01-EU	Final 2.0	Page 35 of 71
Related to PMI-RRP-WKI-112487		

For log-transformed variables, the (relative) change from baseline is defined as: Change from baseline = log(post baseline value / baseline value).

For step count, the baseline will be the average steps taken between V2 and V3.

Time variables, i.e. exercise capacity and time spent at different percentages of maximal work rate (or maximal HR) during each training session will be analyzed in seconds (not in min:sec).

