# 7.6 Exercise Testing and Training

## 7.6.1 VO2max Test and Blood Lactate Levels

Subjects will perform an incremental cycling test to volitional fatigue on an electronically braked cycle ergometer (such as Monark E839, Varberg, Sweden). To measure oxygen uptake and determine VO2max an online gas collection system (e.g. COSMED CPET) will be used where O2 and CO2 concentration in the expired gas are continuously measured and monitored as breath-by-breath values.

Subjects will be asked to refrain from heavy exercise 24h prior to the test, and consuming caffeine or alcohol 12h prior to the test. Measurements will begin with the subjects resting for 3 min seated on the bike ergometer whereafter the workload will be increased by 25W every 60 sec until volitional fatigue. Subjects should keep cadence between 60 and 90 rpm during the test. Mean VO2max will be determined as the highest O2 value averaged over 30 s for each subject. At VO2max the following parameters will be recorded: ventilation (l/min) respiratory rate, VCO2 (l/min), respiratory exchange ratio (RER, [VCO2 / VO2]).

In addition at V4, the maximal heart rate and the maximal work rate will be recorded in order to design the training program.

At V3 and V43, capillary (fingertip or earlobe) blood samples will be obtained at rest and at each 25W workload increased and analysed for lactate (e.g. Radiometer ABL80 or similar). Blood collection should be started 40-45 seconds into the workload and no blood sample should be obtained at maximal effort. The final blood sample should be obtained within 5 minutes after termination of the bike exercise. Heart rate and oxygen uptake (VO2) will be recorded at rest at each 25W increase.

After the test subjects will rest for  $60\pm5$  min and will be offered water *ad libitum* and a light snack e.g. fruit, chocolate or bar. The snack has to be consumed at least 30 min before the upcoming exercise capacity test (not applicable for V1).

Data and information contained in this document are considered to constitute trade secrets and confidential commercial information, and the legal protections provided to such trade secrets and confidential information are hereby claimed under the provisions of applicable law. No part of this document may be publicly disclosed without the written consent of Philip Morris Products S.A

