# 7.10 Mobile Health (mHealth) Wearable

Subjects will wear a mHealth device (Vivofit 3, Garmin), which is worn on the wrist, for the recording of their physical activity including daily step count and intensity minutes. Three intensity levels of physical activity will be recorded; 1) sedentary - little to no activity monitored (e.g. minimal movement, sitting, resting, or sleeping); 2) active – some activity monitored (e.g. a brisk walk); 3) very active- high activity monitored (e.g.running or speed walking).

The wearable will simultaneously record energy expenditure, distance and sleep as described in objective 6, however the analysis and reporting of this data will not be part of the CSR but reported separately.

Data and information contained in this document are considered to constitute trade secrets and confidential commercial information, and the legal protections provided to such trade secrets and confidential information are hereby claimed under the provisions of applicable law. No part of this document may be publicly disclosed without the written consent of Philip Morris Products S.A

Philip Morris Products SA	Clinical Study Protocol	Confidential
P1-EXC-01-EU	Version 3.0 / 2 May 2019	Page 69 of 151

Subjects will be trained on how to wear (i.e. correct positioning) and handle the device in accordance with the user guide. Subjects will be instructed to wear the device on their nondominant wrist and to wear it all the time. As part of the wearable device kit subjects will also receive a mobile phone with Bluetooth and wireless internet connectivity through which data will be transferred from the wearable device. Between V2 and V3, baseline data will be collected, and as of randomization at V3 data will be collected during the investigational period until V43.

The Vivofit 3 device records accelerometer data continuously and transfers data aggregated on a 15-min basis to the data storage cloud. For the parameters to be analyzed as part of the study (objective 5; steps and activity) data transferred from the wearable device to the clinical database will be aggregated on a per 24-hour level. In addition, wear time per day will be monitored. Parameters listed in objective 6 will be transferred from the wearable device on a per 15-min level to the storage cloud. Further details on device set-up, subject account creation, device pairing and mapping, and data flow and storage will be given in a dedicated plan.

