# 9.2 Enrollment and Familiarization with Exercise Test

Visit 2 (V2) will be scheduled 7±1 days prior to V3 (randomization).

Table 6 shows the procedures that will be performed at V2.

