9.6.1.2.5 Daily physical activity

For step count raw values will be averaged and reported by month. Measures of physical activity and changes from baseline will be listed and summarized by visit and actual product use for baseline and each month.

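### SAP 9.1.3 averages V2–V3 for step count only, so read literally the wearable's sedentary, active and very active minutes take a single 24-hour record as baseline

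*SAP*

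**What the plan says.** SAP section 9.1.3 gives one default, "The baseline value for any given parameter will be the last assessment prior to randomization", and one exception for the wearable: "For step count, the baseline will be the average steps taken between V2 and V3". The other three objective 5 endpoint groups (sedentary, active and very active minutes per day, each also as a percentage of time) are not named.

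SAP section 9.6.1.2.5 nevertheless needs a baseline for them: "Measures of physical activity and changes from baseline will be listed and summarized by visit and actual product use for baseline and each month".

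Protocol section 7.10 says of the wearable generally, without limiting it to steps, that "Between V2 and V3, baseline data will be collected". The same section says that for the objective 5 parameters "data transferred from the wearable device to the clinical database will be aggregated on a per 24-hour level", so one record is one day.

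Protocol section 7.6.1 adds, for the VO2max test: "Subjects will be asked to refrain from heavy exercise 24h prior to the test". One such test is done at V3, before randomization.

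**The concern.** A programmer who follows SAP section 9.1.3 as written averages several days for steps but takes one daily record for the activity minutes, then compares that one day with a monthly summary. Two problems follow.

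First, a single day carries its full day-to-day variation into every change score. This widens the SD and the 95% confidence interval that SAP section 9.1.2 asks for in each arm, in arms planned at 25, 25, 25 and 15 subjects.

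Second, neither candidate day is ordinary. The day before V3 overlaps the period in which subjects are asked to avoid heavy exercise. The V3 record holds a VO2max test, an exercise capacity test and some time after randomization. The SAP does not say which of the two is meant, so two programmers could report different changes from the same data.

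**Working it through.** **Does another passage supply a baseline for the minutes?**

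- SAP section 9.1.3.1 defines the wearable's analysis periods from Week 1 onward and gives no baseline period.
- SAP section 9.1.6 defines a valid day (at least 1000 steps), drops the first and last day of data, and asks for 4 valid days per week for weekly averages. It gives no baseline window.
- SAP section 9.6.1.1.5 labels baseline as V2–V3 only for the step-count plots.

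The default in section 9.1.3 is therefore the only SAP rule that reaches the minutes.

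**Noise.** The documents give no SD or day-to-day variance for activity minutes, so there is no planned figure to reproduce, and the variances below are assumptions.

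Inputs:

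- k, the number of full days between V2 and V3. Protocol section 9.2 sets the gap at 7±1 days, so 6 to 8 days, which leaves 5 to 7 full days.
- m = 28 valid days in a month (assumed).
- Total variance of a single day set to 1; ICC between days 0.3 to 0.7 (assumed); within-subject day variance w = 1 − ICC; days independent (assumed).
- τ², the between-subject variance of true change, 0 to 0.5 on the same scale (assumed).

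Variance of one subject's monthly change with a k-day baseline: τ² + w(1/k + 1/m).

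SD ratio, one day against k days: √{[τ² + w(1 + 1/m)] / [τ² + w(1/k + 1/m)]}.

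With τ² = 0, w cancels:

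- k = 5: √(1.0357 / 0.2357) = 2.10
- k = 6: √(1.0357 / 0.2024) = 2.26
- k = 7: √(1.0357 / 0.1786) = 2.41

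With ICC 0.5, τ² = 0.25 and k = 6: √[(0.25 + 0.5 × 1.0357) / (0.25 + 0.5 × 0.2024)] = √(0.7679 / 0.3512) = 1.48.

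Range over k = 5 to 7:

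| ICC | τ² = 0 | τ² = 0.25 | τ² = 0.5 |
|---|---|---|---|
| 0.3 | 2.10–2.41 | 1.53–1.61 | 1.36–1.40 |
| 0.5 | 2.10–2.41 | 1.44–1.50 | 1.28–1.31 |
| 0.7 | 2.10–2.41 | 1.32–1.36 | 1.19–1.21 |

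The choice of m matters little. From the scheduled days of V5, V14, V28 and V43 (15, 40, 68 and 106 after V3), the three months run about 26, 28 and 38 days. For k = 6 and τ² = 0, m = 26 gives √(1.0385 / 0.2051) = 2.25 and m = 38 gives √(1.0263 / 0.1930) = 2.31. Positive correlation between neighbouring days would make averaging less effective and lower the ratios.

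**Direction and size of any shift.**

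- *Very active minutes, day before V3 used.* Less vigorous activity on the baseline day pushes the change up. Exclusion criterion 5 in protocol section 5.1.2 caps vigorous activity at 45 min per week, so the shift is at most about 45/7 = 6.4 min/day, or 6.4/1440 = 0.45% of the day. That ceiling assumes a subject at the cap, no vigorous minutes on that day, and a device category that matches the eligibility wording. With a six-day mean that includes the same zero day, the ceiling is 6.4/6 = 1.1 min/day.
- *Very active minutes, V3 used.* The record contains two exercise tests, so the shift reverses.
- *Sedentary minutes, day before V3 used.* A quieter baseline day has more sedentary time, so the change shifts down.
- *Active minutes.* Protocol section 7.10 gives a brisk walk as the example, which is not heavy exercise, so no direction follows.

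**The case against.** The best reply is that no passage actually prescribes a one-day baseline for activity minutes. The default in SAP section 9.1.3 suits visit assessments, protocol section 7.10 places the wearable's baseline over V2–V3, and SAP section 9.6.1.2.5 sets baseline beside monthly summaries. On this view the omission is a slip of drafting, and the analysts would average the week anyway.

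Part of this stands: the single day is a literal reading of a default, not an explicit instruction. But the SAP carries the protocol's window over by name for steps alone, which implies that the default governs the rest, and nothing in the SAP says otherwise.

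It is also fair that little hangs on these endpoints. The modelled objective 5 endpoint is step count, whose baseline is already the V2–V3 average. The percentages of time active and very active are summarized descriptively, and the study tests no hypothesis. That limits the consequence without removing the inconsistency.

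A reader might go further and infer that the changes are biased upward, or that a false rise in activity could pass for a benefit of switching. The documents support neither. The sign depends on the measure and on which day is used. The baseline also precedes randomization and the exercise restriction applies to everyone, so any shift should be similar across randomized arms.

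**Conclusion.** The point holds as an inconsistency in the baseline rule, with a real but modest effect. Followed literally, SAP section 9.1.3 gives sedentary, active and very active minutes a one-day baseline where the protocol collected a week of data.

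The cost in precision is an SD of change about 1.2 to 1.6 times larger when true change varies between subjects, rising to 2.1 to 2.4 only if it does not vary at all. That last case is hard to credit in a trial that mixes trained and untrained arms. All of these ratios rest on assumed variances and independent days.

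The baseline day is unrepresentative whichever record is taken, but no general direction of bias is established. For very active minutes the upward shift is at most about 6.4 min/day, and only if the day before V3 is used. What is mainly affected is the within-arm descriptive change, where a shift common to all arms does not cancel.

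**What to change.** In SAP section 9.1.3, replace the step-count sentence with one that covers every mHealth parameter (steps; sedentary, active and very active minutes; percentage of time in each). Baseline would be the mean over valid days from the day after V2 to the day before V3, with a stated minimum, for example 4 valid days, in line with the weekly rule in SAP section 9.1.6. This also settles that the V3 day is left out.

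The restricted day before V3 stays in the window, but as one day among 5 to 7. The change costs one sentence and no new data. The downside is that a few subjects with too few valid baseline days would have no change score; their number should be reported.
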